#### Fat Liver Content Change from Baseline:

The current sample size of 40 subjects per group should yield approximately 85% power to detect a treatment effect of at least -5% with respect to the difference in the mean change from Baseline between one of the IMM-124E treatment groups and placebo assuming a standard deviation (SD) of 7.3% ( $\alpha=0.05$ ; two-tailed; unpaired t-test). The SD of 7.3% for the change from Baseline endpoint was derived assuming 1) SDs of 6% for each timepoint, 2) equal variances in each treatment group and 3) a low to moderate correlation of 0.25 between pre- and post-Baseline measurements.

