## 12.4 Statistical Analysis Plan

A detailed SAP in which all aspects of data analysis will be defined in detail and prepared prior to the blind break.

The SAP will include details of the following:

- Definitions of analysis populations
- Description of any data transformations and data derivations to be used together with rationale and references
- Details of the statistical methods to be conducted, together with methods used to estimate corresponding confidence intervals
- Details of methods for checking the appropriateness of the chosen statistical model
- Discussion of the use of covariates and subgroups
- Discussion of any multiplicity and adjustment procedures to be implemented.
- Methods of dealing with missing values and outliers together with details of any sensitivity analyses to be performed
- Specification of any subgroup or interaction analyses
- Example table and listing shells to indicate the proposed presentation of the data.

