3.4 Data handling

Data collected during the course of this study have been entered into an IBM Clinical Development formerly known as eClinical OS (eCOS) electronic clinical record database, which is a commercially available database (Merge, now an IBM company) specifically designed for such use. Data is entered into the database at each study centre. SAS datasets are one of the outputs of the database. Following review, validation and correction of the data entered into the database, a meeting will be held to declare the file to be clean and proceed to data lock, after which no changes to the data are possible. At the Clean File meeting, analysis populations will be discussed and finalised. Following the signing of the Clean File document by all signatories, the randomisation code will be broken following Datapharm Australia standard operating procedures set for that activity.

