7.2 Primary efficacy analyses

The hepatic fat fraction will be summarised and tabulated for the Baseline and Week 24 visits along with change from Baseline by randomised treatment group. Change in hepatic fat fraction from Baseline will be analysed using analysis of variance on the ITT, PP and FAS populations, where the model will include the treatment group and another subgrouping variable. As determined by baseline values, hepatic fat fraction categories ($\leq 10\%$, $>10\% - <21\%$, $\geq 21\% - <30\%$ and $\geq 30\%$), HbA1c group ($< 6\%$ and $\geq 6\%$), and ALT (greater or less than 1.5 x the upper normal limit) will be used to subgroup the analysis populations. Further, data from liver biopsies up to 6 months prior to screening will also be used to subgroup analysis populations based on fibrosis (0-1 vs. 2-3), NAS inflammation (0-1 vs. 2-3), and NAS ballooning (0-1 vs. 2). These will be used in addition to the main effects factors and the two-way interaction of those main effects.

In the primary analysis, any missing data will remain missing. Treatment effects between placebo and each of the active treatment groups within each of the hepatic fat and HbA1c categories will be generated and tested for significant differences between treatment and placebo using pre-specified contrasts.

To examine the effect of treatment within the various levels of these subgroup variables, a mixed models ANOVA will be employed if there are an appropriate number of observations in each cell (created by the crossing of study treatment and subgroup categories) and the data does not differ significantly from a normal distribution. In the event that this is not the case, the data will be ranked in an attempt to normalise it, and pairwise contrasts between treatment groups will be performed using Wilcoxon rank sum tests within each combination of visit and subgroup variable level will be performed. However, if the ranked data is also not normally distributed, a permutation test will be employed whereby the unranked data will be randomly sampled (Lehmann, 2006). No adjustment for multiple testing will be made. See Appendix 1 for more information on both the Wilcoxon rank-sum test and the permutation test.

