Sensitivity analyses will be performed in the final study analysis and will use the same analysis method on the FAS and PP populations using the multiple imputation and analysis method to impute missing values and, finally, an analysis using the full set of ITT population data, but including study centre as an additional main effect.

Interaction effects with study centre will not be investigated. If any outliers are detected (defined as greater than ± 2 SD away from the mean for that group and visit combination), sensitivity analyses will be performed where those outliers are removed and then will be compared with the analysis where those outliers were not taken out.

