9. INTERIM ANALYSES

An interim analysis is planned when 80 subjects have completed the full 24 week study period. The analysis population will include data from those 80 subjects up to and including week 24, in addition to all early terminations (up to and including week 24) and all remaining currently randomised subjects with post-baseline data prior to the 28th of February 2017. Populations in the interim analysis will use the same definitions as the full analysis at the end of the study.

The purpose of this interim analysis will be to establish the safety of the study treatment, identify signals of efficacy of the two dose groups (600mg and 1200mg) against Placebo and to set sample size parameters for potential future studies. As a result, the critical probability for the interim analysis will be 0.00305, which requires the final alpha level to be 0.04695. All populations will be analysed for the interim analysis as described above.

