Hepatic fat fraction with HbA1c sub-groups as stratification factor (FAS population)

Hepatic fat fraction with HbA1c sub-groups as stratification factor (PP population)

Hepatic fat fraction with Inflammation sub-groups as stratification factor (ITT population)

Hepatic fat fraction with Inflammation sub-groups as stratification factor (FAS population)

Hepatic fat fraction with Inflammation sub-groups as stratification factor (PP population)

Hepatic fat fraction with ALT sub-groups as stratification factor (ITT population)

Hepatic fat fraction with ALT sub-groups as stratification factor (FAS population)

Hepatic fat fraction with ALT sub-groups as stratification factor (PP population)

Hepatic fat fraction with outliers excluded (ITT population)

Hepatic fat fraction with outliers excluded (FAS population)

Hepatic fat fraction with outliers excluded (PP population)

ALT area under the curve values for 24 weeks of treatment (ITT population)

ALT area under the curve values for 24 weeks of treatment (FAS population)

ALT area under the curve values for 24 weeks of treatment (PP population)

ALT area under the curve values for 24 weeks of treatment with hepatic fat fraction sub-groups as stratification factor (ITT population)

ALT area under the curve values for 24 weeks of treatment with hepatic fat fraction sub-groups as stratification factor (FAS population)

ALT area under the curve values for 24 weeks of treatment with hepatic fat fraction sub-groups as stratification factor (PP population)

ALT area under the curve values for 24 weeks of treatment with HbA1c sub-groups as stratification factor (ITT population)

ALT area under the curve values for 24 weeks of treatment with HbA1c sub-groups as stratification factor (FAS population)

ALT area under the curve values for 24 weeks of treatment with HbA1c sub-groups as stratification factor (PP population)

ALT area under the curve values for 24 weeks of treatment with Fibrosis sub-groups as stratification factor (ITT population)

ALT area under the curve values for 24 weeks of treatment with Fibrosis sub-groups as stratification factor (FAS population)

ALT area under the curve values for 24 weeks of treatment with Fibrosis sub-groups as stratification factor (PP population)

ALT area under the curve values for 24 weeks of treatment with Ballooning sub-groups as stratification factor (ITT population)

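### The SAP 7.2 outliers-removed sensitivity analysis trims each arm at ±2 SD of its own mean, so its overall active-versus-placebo p-values are too small (about 6.5-8.5% null rejection at the planning values, against 4.7%)

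*SAP*

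**What the plan says.** SAP 7.2 analyses change in hepatic fat fraction by analysis of variance, "where the model will include the treatment group and another subgrouping variable", with their interaction, and also specifies active-versus-placebo contrasts inside the fat and HbA1c categories. It then defines an outlier as a value "defined as greater than ± 2 SD away from the mean for that group and visit combination" and states that "sensitivity analyses will be performed where those outliers are removed and then will be compared with the analysis where those outliers were not taken out". SAP 12 lists the resulting tables for the ITT, FAS and PP populations. Its sample shells for the primary analysis have probability columns.

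The final significance level comes from SAP 9, "which requires the final alpha level to be 0.04695". The rule acts on data that have already been checked: under SAP 3.4, "Following review, validation and correction of the data entered into the database, a meeting will be held to declare the file to be clean". Protocol 12.4 asks the SAP for "Methods of dealing with missing values and outliers together with details of any sensitivity analyses to be performed".

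The SAP does not say whether Week 24 alone or both visits are screened, whether the group is the treatment arm or an arm-by-category cell, or whether the flagged value or the whole subject is removed.

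**The concern.** A ±2 SD rule does not isolate aberrant values. Ordinary normal data trip it routinely, and because queries and corrections come before data lock, most of what it removes will be genuine measurements. Cutting both tails of each arm around that arm's own mean lowers the residual SD. The difference between arm means does not become more precise; its true sampling variability rises slightly. The usual ANOVA standard error then understates the uncertainty.

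What is at stake is the fairness of the robustness check. Its only stated use is comparison with the undeleted result. If p-values are compared, a result that looks stronger after deletion may be an artefact of the rule.

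**Working it through.** **Inputs.** From Protocol 12.1: 40 per arm, SD 6 at each visit, "a low to moderate correlation of 0.25 between pre- and post-Baseline measurements", two-sided test. From SAP 9: alpha 0.04695. From SAP 7.2: fat categories ≤10, >10-<21, 21-<30 and ≥30%. Assumed, because the documents do not give them: mean baseline fat 15, 18 or 22%; group means treatment arm; a flagged subject leaves the change analysis; HbA1c groups split 50/50.

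**The plan's own figures.** SD of change = √(2 × 6² × (1 − 0.25)) = √54 = 7.35 (stated 7.3). Power for a difference of 5 at two-sided 0.05, noncentral t on 78 df, is 85.7% with SD 7.3 and 85.2% with 7.35. The stated 85% is reproduced. The documents give no error rate for the trimmed analysis.

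**How many are flagged with no true outliers.** With 40 per arm, about 4.1% of normal values lie beyond 2 sample SD: 0.041 × 120 = 4.9 subjects. With both visits screened, about 7.95% of subjects are flagged: 0.0795 × 120 = 9.5. At least one is flagged in about 99.9% of trials.

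**Null rejection, bivariate normal data, no treatment effect.** The overall contrast with fat category comes from 20,000 trials per setting (Monte Carlo SE about 0.2 points), the one without from 60,000 (about 0.1 points).

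| Active-versus-placebo contrast, r = 0.25 | Undeleted | Week 24 screened | Both visits screened |
|---|---|---|---|
| Overall, fat category in model (baseline mean 15 / 18 / 22%) | 4.8 / 4.6 / 4.8% | 8.6 / 8.8 / 8.4% | 8.6 / 8.7 / 8.5% |
| Overall, no category (planning t-test) | 4.9% | 6.5% | 8.6% |
| Within >10-<21% fat (mean 18%) | 4.9% | 7.2% | 7.2% |
| Within 21-<30% fat (mean 18%) | 4.5% | 5.5% | 5.5% |
| Within HbA1c group | 4.2-4.9% | 5.0-5.3% | 6.5% |

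Further runs give up to 7.5% in the >10-<21% category, 5.2-5.7% in 21-<30% and up to 6.7% for HbA1c groups. In the sparse end fat categories rejection is at or below nominal (3.8-4.3% for ≤10%).

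**Why.** In the fat-category model (mean 18%) the true SD of the estimated difference rises from 1.40 to 1.52 (Week 24) or 1.55 (both visits). The average model SE falls from 1.39 to 1.30 or 1.33. The normal critical value for 0.04695 is 1.987, so the effective cut is 1.987 × 1.30 / 1.52 = 1.70, a two-sided rate of about 8.9%, or 1.987 × 1.33 / 1.55 = 1.70, about 8.8%. Both agree with the simulation. The mean difference stays near zero (−0.013 and −0.009, against −0.006 undeleted), so the estimate is not biased under the null.

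**Direction of the comparison.** In the same setting deletion turns a non-significant result significant in 4.98% of trials and does the reverse in 0.77% (Week 24): 4.98 / 0.77 = 6.5. With both visits screened: 5.01 / 0.93 = 5.4. Across runs the ratio is roughly 4.5 to 6.5. Significance in both versions occurs in 3.7-3.8% of null trials, so that joint finding is not inflated.

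**Sensitivity.**
- Assumed r = 0.8, visit values screened: about 6-6.6% with fat category, 5.1-5.8% without.
- Heavier tails (t, 5 df): 7.6-7.8% with fat category; skewed gamma: 7.9-8.0%.
- Trimming within arm-by-fat-category cells: 6.5-8.9%.
- A 3 SD cut with fat category: about 5.0% against 4.7% undeleted. It flags about 0.2 of 120 subjects (Week 24) or 0.35 (both visits).

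**The case against.** The strongest reply is that little depends on these tables. They are sensitivity output in a trial the protocol calls exploratory, multiplicity is openly unadjusted, and SAP 7.2 neither attaches a decision rule nor says the comparison is by p-value. Comparing the two point estimates remains valid. All of that stands, and it is why the point is minor. It does not make the p-values right: forgoing multiplicity adjustment accepts many tests, but each should still run near its nominal level.

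It is also fair to say that no single rate describes the whole analysis. A reader might take 8-9% as applying to every contrast. SAP 7.2 specifies within-category contrasts too, and most of those are inflated much less or not at all. A reader might prefer the roughly 10% found when change itself is screened in a model without category, but the SAP wording refers to values at a visit, so that is the reading furthest from the text.

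Finally, a reader might conclude that the planned confidence intervals are wrong. The sample shells show no interval for the treatment difference, and Protocol 12.5 mentions intervals only about group means. Any interval built from the trimmed data would share the fault (nominal 95% coverage of 93.2% or 91.0% in the t-test setting, against 94.8% undeleted), but the shells do not show one.

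**Conclusion.** The point holds, as a minor one. At the planning values the ±2 SD rule raises null rejection for the overall active-versus-placebo contrast from about 4.7% to about 8.5% with fat category in the model, and to 6.5-8.5% without it. Within categories the figures are about 7.3% (>10-<21% fat), 5.5-5.7% (21-<30%) and about 5-6.7% (HbA1c groups), with no inflation in the sparse end categories. The roughly 4.5- to 6.5-fold tilt towards significance applies to the additive model at r = 0.25.

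These sizes rest on the assumed baseline means, the 50/50 HbA1c split, trimming by arm and removal of the subject. The inflation shrinks as the correlation between visits rises.

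It would be wrong to infer that the trial's own error rate is inflated. The primary analysis has no deletion rule and keeps its nominal level.

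**What to change.** Report the three outliers-excluded tables as point estimates beside the undeleted ones, with a listing of flagged subjects and no inferential p-values, or any intervals, from the trimmed data. If an inferential version is wanted, use a cut of about 3 SD instead.

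In either case state which variable is screened (Week 24 value, both visits, or change), whether the group is the treatment arm or a subgroup cell, and whether the value or the subject is removed.

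This is SAP wording only, with no new data, and either option still meets the Protocol 12.4 request for an outlier method. The cost is the loss of p-values in three sensitivity tables. With the 3 SD cut the p-values are kept, but the check removes almost nothing in normal data (about 0.2-0.4 of 120 subjects).

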7.3 Secondary efficacy analyses

The following analyses of secondary efficacy will be performed on the FAS population. However, if the results for the primary efficacy analysis differ across populations, the ITT and PP populations may also be subject to secondary efficacy analysis. For the analyses detailed in this section and section 7.4, inferential statistical analysis will be performed on the same basis as for the primary endpoint. For those values that are recorded at 3 or more time-points, the baseline value will be included in the repeated measures analysis as a covariate. For analyses with only a baseline and final value, t-tests or Wilcoxon rank-sum tests will be performed depending on the distribution of the data. In addition to this, the mean change from baseline for all relevant variables will be assessed and presented.

Serum concentrations of IMM-214E bovine antibodies (including but not limited to: maximum and minimum observed concentration, area under the concentration-time curve, and (if feasible) elimination half-life) will be summarised and tabulated by visit and time point. Pharmacokinetic coefficients, including but not limited to, maximal and minimal concentration, area under the concentration curve and, if possible, elimination half-life will also be summarised and tabulated with change from Baseline by visit.

Body mass index (BMI), waist circumference and waist:hip ratio with change from Baseline will be summarised and tabulated by visit and treatment group.

HbA1c, glucose and homeostatic model assessment of insulin resistance (HOMA-IR) will be summarised and tabulated with change from Baseline by visit and treatment group.

Serum lipid profile values of total cholesterol, triglycerides and high and low density lipoproteins with change from Baseline and number of clinically significant values will be summarised and tabulated by visit and treatment group. Liver function values of ALT, AST, GGT, bilirubin and albumin, with change from Baseline will be summarised and tabulated by visit and treatment group. These liver function tests will also be correlated with HFF, CRP, and A1c. The proportion of subjects with ALT within the normal reference range at Week 24 will be summarised and tabulated by treatment group. Logistic regression modelling will be used to compare proportions in the Placebo group against each of the IMM-124E treatment dose groups using the same model used in the primary efficacy analysis, although the Baseline value of the liver function analyte will be used as a covariate. The area under the curve for change

from Baseline to Week 24, using the Baseline value as reference, for liver enzymes ALT, AST and GGT will also be analysed. For patients in the FAS population who withdraw prior to Week 24, the area under the curve will be adjusted in a manner comparable to a full 24 week period value.

The proportion of subjects demonstrating a decrease in liver percent fat at 24 weeks compared to baseline of 5%, 10%, 20% and 30% respectively will also be analysed. In a similar manner, proportional decreases in ALT, AST and A1c will be assessed using appropriate percentages.

Correlations between change in hepatic fat fraction and changes in ALT, C-reactive protein and A_{1c} will also be calculated.

The Fibrosis-4 Score will be calculated at each visit for which there is data. The formula is $FIB-4 = (Age * AST) / (Platelets / \sqrt{ALT})$. This score will be summarised and tabulated in the same manner as the primary endpoint.

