
Sample size determination:
	
Fat Liver Content Change from Baseline:                  The current sample size of 40 subjects per group should yield approximately 85% power to detect a treatment effect of at least -5% with respect to the difference in the mean change from Baseline between one of the IMM-124E treatment groups and placebo assuming a standard deviation (SD) of 7.3% (<math>\alpha=0.05</math>; two-tailed; unpaired t-test). The SD of 7.3% for the change from Baseline endpoint was derived assuming 1) SDs of 6% for each timepoint, 2) equal variances in each treatment group and 3) a low to moderate correlation of 0.25 between pre- and post-Baseline measurements.
 
Sample size and power estimates have not been adjusted for multiple comparisons or multiple endpoints, dropouts or stratification.
 
The analysis of each primary endpoint will be based on a linear model that incorporates the baseline measure as a covariate, the stratification factor and randomized treatment group. Pairwise comparisons of each active treatment group to control will be conducted via linear contrasts.

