2.2 Study design

This was to be a randomized, double blind, placebo controlled, 3-arm parallel group, multi-dose, multi-centre study. The three treatment arms include 600mg IMM-124E three times daily, 1200mg IMM-124E three times daily and matching placebo. A total of 120 subjects, randomised to the three treatment groups in 1:1:1 ratio, having been previously diagnosed with NASH will be studied during a 24 week treatment period.

An interim analysis will be planned for this study, the purpose of which will be to determine whether any safety concerns exist as well as identify any preliminary signals for efficacy through examination of the primary, secondary and exploratory endpoints. The interim analysis will occur when 80 subjects have completed the 24 weeks treatment period and have both Baseline and 24 weeks' evaluable MRI hepatic fat fraction values. Each IMM-124E dose group will be compared to the placebo treatment group using pairwise contrasts. This analysis will occur for each of the hepatic fat fraction strata because of a differential response pattern across strata that have been noticed in previous studies on NASH (Le et al., 2012; Loomba et al., 2015).

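### The logistic model for normal ALT at Week 24 inherits the treatment-by-subgroup interaction; in its liver-fat version that means 12 cells of about 10 patients, a material risk of separation, and no rule for handling it

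*SAP*

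**What the plan says.** SAP 7.3 assigns logistic regression to the comparison of placebo with each dose on ALT within the normal range at Week 24. The model is defined by reference: "using the same model used in the primary efficacy analysis", with the baseline liver-function value as a covariate.

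SAP 7.2 describes the primary model as an analysis of variance "where the model will include the treatment group and another subgrouping variable". It lists six subgrouping variables and adds: "These will be used in addition to the main effects factors and the two-way interaction of those main effects". HFF has four levels. HbA1c, ALT, fibrosis, inflammation and ballooning have two each.

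SAP 7.2 also has a condition on cell numbers and a fallback to ranks and then permutation, but both are written for a continuous outcome. Neither document says what happens if the logistic model meets a cell with no responders or only responders. No estimation method is named beyond logistic regression.

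The output list in SAP 12 has normal-ALT tables by HFF subgroup, and by each other subgroup, for the FAS, ITT and PP sets. It also has normal-ALT tables with no subgroup factor.

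On size, SAP 2.2 gives "A total of 120 subjects, randomised to the three treatment groups in 1:1:1 ratio". The protocol synopsis states: "Sample size and power estimates have not been adjusted for multiple comparisons or multiple endpoints, dropouts or stratification".

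**The concern.** A logistic model with a full treatment-by-subgroup interaction fits each cell almost freely. If every patient in a cell responds, or none does, the likelihood keeps rising as that cell's parameter goes to infinity. This is separation. The baseline covariate does not prevent it, because the cell indicator alone is enough to cause it.

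In a stratum with one such cell, the dose-versus-placebo odds ratio runs to zero or infinity; if both cells are empty of responders it is undefined. A dose effect averaged over strata takes in the divergent term. Wald tests on divergent estimates are uninformative.

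This logistic model is the only inferential method that SAP 7.3 names specifically for ALT normalisation, which Protocol 4.2 lists as a secondary endpoint. With no rule written in advance, a substitute model would probably be chosen when the problem appears, after unblinding.

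**Working it through.** **The plan's own figure.** The documents give no figure for the logistic models. The only stated power concerns liver fat: "The current sample size of 40 subjects per group should yield approximately 85% power to detect a treatment effect of at least -5" percentage points, "assuming a standard deviation (SD) of 7.3" percent, "two-tailed; unpaired t-test". It reproduces. The SD of change is √(6² + 6² − 2 × 0.25 × 6 × 6) = √54 = 7.35. With 40 per arm, difference 5 and SD 7.3, the noncentral t with 78 df gives 85.7% (85.2% with SD 7.35). It says nothing about binary endpoints.

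**Inputs.** From the documents: 120 patients, 40 per arm; 3 arms × 4 HFF levels = 12 cells, mean 120/12 = 10; at the interim 80/12 = 6.7. Assumed, because the documents do not give them: the response rate p, taken as equal in all cells, and the HFF stratum shares.

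**Formula.** A cell of size n is all-or-none with probability (1−p)^n + p^n. Over independent cells,

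P(at least one) = 1 − Π[1 − (1−p)^n − p^n].

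*Equal strata, n = 10, p = 0.20:* 0.8^10 = 0.1074 and 0.2^10 is negligible, so P = 1 − 0.8926^12 = 74%.

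*Strata 10/40/40/10%, n = 4, 16, 16, 4 per arm, p = 0.30:* for n = 4, 0.2401 + 0.0081 = 0.2482; for n = 16, 0.0033. P = 1 − 0.7518^6 × 0.9967^6 = 82%.

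| Model | Cells | p = 0.10 | 0.20 | 0.30 | 0.50 |
|---|---|---|---|---|---|
| HFF interaction, equal strata | 12 of 10 | 99% | 74% | 29% | 2% |
| HFF interaction, 10/40/40/10% | 4, 16, 16, 4 per arm | >99.9% | 96% | 82% | 55% |
| HFF interaction, equal strata, interim | 12 of 7 | >99.9% | 94% | 64% | 17% |
| Two-level subgroup interaction, equal cells | 6 of 20 | 54% | 7% | 0.5% | <0.1% |
| No subgroup | 3 of 40 | 4.4% | <0.1% | <0.1% | <0.1% |

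**Which strata are plausible?** Equal strata would put 25% of patients at or below 10% fat and 25% at or above 30%. The smallest SD compatible with that has the other half at 20%: √(0.25 × 10² + 0.25 × 10²) = 7.1. The protocol's planning SD is 6% at each timepoint, so equal strata do not fit it.

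If baseline HFF were also roughly normal (a further assumption), at least one outer stratum would hold no more than Φ(−10/6) = 4.8% of patients, about 2 per arm. Simulating that case for means of 15% to 25% puts the probability of a non-empty all-or-none cell above one half at every rate from 10% to 50%. It is lowest, at about 55% to 65%, for a mean of 15% or 25% and a rate of 50%. At a mean of 20% it is 98% or more.

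**Effect of dropping the interaction.** Separation was tested by linear programming in simulated trials: 120 patients, 400 runs per setting, one baseline covariate with an assumed log-odds slope of 1 per SD, and HFF as the only stratification factor. Rates are for p = 0.10, 0.20 and 0.30.

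| Strata | With interaction | Main effects only |
|---|---|---|
| Equal | 99.5%, 71%, 33% | 19%, 0.3%, 0% |
| Assumed 10/45/30/15% | 99.8%, 94%, 74% | 43%, 9%, 2% |

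Most of the problem goes, but not all of it at low response rates. That is why a penalised likelihood is still needed.

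**The case against.** The strongest reply is that an overall comparison without subgroups seems to be planned. SAP 12 lists normal-ALT tables with no subgroup factor, and the sample shells separate a primary analysis from one with subgrouping. If the overall table uses treatment alone, an all-or-none arm has probability 4.4% at a 10% rate and below 0.1% at 20%. This stands in part: a reader might infer that the whole ALT comparison is unusable, and the documents do not support that. But SAP 7.3 defines its logistic model by reference to one that contains the interaction, and no separate overall logistic model is written down.

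A reader might also infer that separation is almost certain. The documents give neither a normal-ALT rate nor an HFF distribution, so this cannot be derived. The current eligibility criteria set no minimum ALT, so a low rate of normal ALT cannot be presumed. With equal strata and a 50% rate the risk is 2%.

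Three further limits are fair. Only one of the six subgroup variables has four levels. Only contrasts that involve an all-or-none cell, or that average over strata, diverge. The logistic sentence concerns normal ALT; for the liver-fat and proportional ALT, AST and HbA1c responders, logistic regression is only inferred from the general rule that secondary analyses follow the primary.

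Finally, this is a secondary endpoint in a trial that Protocol 12 calls exploratory. That limits the consequence, but it does not supply the missing rule.

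**Conclusion.** The concern holds for normal ALT at Week 24 in the HFF version of the model. The SAP's wording carries the interaction into a logistic regression with 12 cells averaging 10 patients, and no sparse-cell rule applies to it. The risk of at least one all-or-none cell runs from 2% to over 99.9% across the assumed rates and the two stratum patterns. Under strata consistent with the protocol's own SD, and a roughly normal baseline, it is more likely than not at rates of 10% to 50%. For the two-level subgroups it is a minor risk unless the response rate is near 10%.

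The conclusion rests on an assumed common response rate and assumed stratum shares. It does not extend to all responder endpoints, to every stratum's estimate, or to a comparison made without subgroups.

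**What to change.** State in SAP 7.3 that each dose is compared with placebo on normal ALT at Week 24 by a logistic model with treatment, the stratification factors and baseline ALT, without the interaction, fitted by Firth penalised likelihood as the main analysis. Report a stratified Mantel-Haenszel risk difference for each dose versus placebo as supportive. Give response rates by HFF subgroup descriptively. If the other responder endpoints are to be tested, apply the same model, with each endpoint's own baseline value.

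This matches the structure of the linear model in the protocol synopsis, which has baseline, stratification factor and treatment and no interaction. The cost is SAP wording, settled before unblinding; Firth estimation is available in SAS 9.4, the version the SAP names. The downside is that binary endpoints lose a formal test of treatment-by-subgroup interaction.
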